10.6 Analyses

A Statistical Analysis Plan will be developed that describes, in detail, the analyses to address the study's primary and secondary objectives. The following provides an outline of the methods for the main comparisons between randomized arms, particularly for the primary outcome measure.

All analyses involving randomized comparisons will include all randomized participants who received the first (confirmed) dose of study treatment, according to a modified intention-to-treat approach. This is motivated by the fact that consent/eligibility confirmation and randomization may occur remotely, prior to the study entry visit. For those who opt to have an in-person entry visit, it is possible that some randomized individuals will not show up. Additionally, it is possible (though unlikely) that some participants show up for the in-person study entry visit, but then decline study treatment. For participants who have a remote entry visit, confirmation of the first dose of study treatment is required.

10.6.1 Primary Outcome Measure

The cumulative proportion of participants hospitalized or dying during the first 21 days of follow-up will be estimated for each randomized arm, in each risk stratum, using Kaplan-Meier methods to take account of losses to follow-up. For each stratum, the difference between randomized arms in the estimated log cumulative proportion will be calculated and the variance for this difference will be obtained using Greenwood's formula. To compare the outcome in the overall study

population, the stratum-specific estimated differences in log proportion will be combined across strata, weighted by the inverse of the stratum-specific variance of the difference. Two-sided 95% confidence intervals (adjusted for multiple interim analyses), based on this weighted estimator, and associated p-value for the test of no difference between arms will then be obtained.

Participants who prematurely discontinue the study, who are not able to be contacted by the site to ascertain outcomes after discontinuation, will have follow up censored at the date of last known status.

The above analysis assumes that losses to follow-up are non-informative. As a sensitivity analysis of this assumption, causal inference methods, specifically inverse probability of censoring, may be used. These methods may also be used to evaluate the sensitivity of results to crossover of treatment in the placebo arm (i.e., participants taking HCQ and/or Azithro from sources outside of the study).

To evaluate the potential impact of multiple participants enrolling from the same household on the primary inference an additional sensitivity, analysis will restrict to the first person enrolled from each household. If differences are observed, additional considerations will be given to analyses that account for clustering, for example, bootstrap methods to estimate the variance of difference in the primary outcome between randomized arms.

10.6.2 Secondary Outcomes

The cumulative proportion of participants dying during the first 21 days of follow-up, and through to 24 weeks, and the cumulative proportion hospitalized/dying through to 24 weeks will be analyzed in a similar manner to the primary outcome.

Tolerability (occurrence of premature discontinuation of study treatment due to an adverse event) will be evaluated by estimating the proportion of participants who discontinue study treatment, and will be compared between arms using binary regression with adjustment for a participant's risk stratum. The proportion of participants who experience cardiac adverse events will be analyzed in a similar manner.

Duration of fever, duration of symptoms and duration of time to self-reported return to usual health will be summarized with descriptive statistics. Participant-specific durations of fever and symptoms will be compared between study arms using a two-sided stratified Wilcoxon test with a 5% Type I error rate. Total symptom score will be calculated on each day and the participant-specific area under the curve (AUC) over time will also be compared using a two-sided stratified Wilcoxon test. Participants who do not have complete diary cards due to hospitalization or death will be ranked in these analyses as having poorer outcomes than participants who survived without hospitalization.

The comparison of the proportion of participants with detectable SARS-CoV-2 RNA will use binary regression, with adjustment for risk stratum and pre-treatment SARS-CoV-2 RNA level. The model will be fitted using generalized estimating equations (GEE) to handle the repeated measurements, where the comparison between randomized arms will use a two-sided Wald test. Levels of SARS-CoV2 RNA levels will be compared between arms using non-parametric Wilcoxon rank-sum tests, separately at Day 6 and Day 20, considering results below assay limit as the lowest rank.

Descriptive summaries of clinical outcomes among those hospitalized will be provided by arm, recognizing that this would not be a randomized comparison, if restricted to participants who were hospitalized.

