10.2.2 Secondary Outcome Measures

- 10.2.2.1 Death from any cause during the 21-day period from and including the day of the first (confirmed) dose of study treatment.
- 10.2.2.2 Death from any cause or hospitalization or urgent visit to an emergency room or clinic during the 21-day period from and including the day of the first (confirmed) dose of study treatment.
- 10.2.2.3 Death from any cause or hospitalization during the 24-week period from and including the day of the first (confirmed) dose of study treatment. Hospitalization is defined as requiring at least 24 hours of acute care in a hospital or similar acute care facility, including Emergency Rooms or temporary facilities instituted to address needs during the COVID-19 pandemic. Evaluation at a hospital or similar facility with less than 24 hours of acute care is not considered a hospitalization.
- 10.2.2.4 Premature discontinuation of study treatment due to an adverse event.
- 10.2.2.5 Occurrence of any cardiac adverse events from start of study treatment through Day 20.
- 10.2.2.6 Duration of fever defined as the last day in the participant's daily diary card on which a temperature greater than 100.4°F was recorded or a potentially antipyretic drug, such as acetaminophen or ibuprofen, was taken.
- 10.2.2.7 Duration of symptoms associated with COVID-19 disease defined as the last day in the participant's daily diary card on which a moderate or worse symptom was recorded. The set of targeted symptoms are the same ones that are used in many influenza studies, with the addition of the symptoms of loss of smell and loss of taste, which have been associated with COVID-19 infection. The symptoms from influenza studies are: cough, shortness of breath, feeling feverish, fatigue, muscle aches, diarrhea, vomiting, nausea, headache, sore throat, nasal obstruction (stuffy nose), and nasal discharge (runny nose). These symptoms are listed individually on the Study Diary that each participant will complete each day. The scoring is that used in influenza studies, whereby participants grade each symptom as absent (score 0), mild (1), moderate (2), or severe (3).
- 10.2.2.8 **Participant-specific area under the curve (AUC) of the symptom**

score associated with COVID-19 disease **over time (through Day 20)** defined as the sum of scores for the targeted symptoms (defined above) in the participant's daily diary record (each individual symptom is scored from 0 to 3).

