10.4 Sample Size and Accrual

The proposed sample size is 2000 participants who take the first (confirmed) dose of study treatment (approximately 1000 per arm). Participants who are randomized but do not take the first (confirmed) dose of study treatment will not be followed and will be replaced.

The study accrual rate will depend on the status of the epidemics at each site, but based on a survey of possible sites is believed to be 100 to 400 participants per week.

- With 100 participants per week the study should fully accrue in 20 weeks
- With 200 participants per week the study should fully accrue in 10 weeks
- With 400 participants per week the study should fully accrue in 5 weeks

The study is designed to evaluate the efficacy of HCQ and Azithro to prevent hospitalizations and death in outpatient adults diagnosed with COVID-19 compared to those receiving placebo. The primary analysis will include testing the null hypothesis of equality of proportions hospitalized/dying in the two randomized arms, and construction of 95% confidence intervals (CIs) for the ratio of proportions between the study arms. The primary analysis will focus on comparing the ratio of proportions because of the uncertainty in knowing what the hospitalization/death rate will be.

With 2000 participants, the study has 90% power to detect a relative reduction of 33.3% in the proportion of participants hospitalized/dying between the study arms (HCQ and Azithro vs. placebo), using the following assumptions:

- Proportion hospitalized/dying in the placebo arm is 15%
- Two-sided test of two proportions with 5% Type I error rate
- Three interim analyses and one final analysis, equally spaced, with stopping guideline determined using the Lan-DeMets spending function approach with an O'Brien and Fleming boundary.
- Allowance for 5% of participants to be lost-to-follow-up prior to being hospitalized or dying.

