10.5 Data and Safety Monitoring

A NIAID-appointed Data and Safety Monitoring Board (DSMB) will undertake reviews of interim data from the study to help ensure the safety of participants in the study, and to recommend changes to the study including termination or modification for safety reasons

or if there is persuasive evidence of efficacy or lack of efficacy of HCQ and Azithro versus placebo in preventing hospitalizations and deaths. The DSMB may also recommend termination or modification of the study if it appears futile on operational grounds to continue the study as designed. The operation of the DSMB is governed by the NIAID DSMB Charter.

To monitor for potential cardiac safety issues, the DSMB will be notified of cases of TdP, ventricular arrhythmias and sudden deaths (with treatment assignment), as the study team becomes aware of them.

At each interim review, the DSMB will review summaries of data by randomized treatment arm for the primary outcome of hospitalization/death, losses to follow-up, adverse events, self-report of treatment cross-over, and the secondary outcomes of death, study treatment discontinuations and associated reasons, duration of symptoms of COVID-19 disease and duration of fever. By-stratum summaries will also be reviewed.

There will be a review of safety data by the DSMB when 250 participants have completed Day 20 of follow-up. Unless otherwise recommended by the DSMB, interim analyses of both safety and efficacy data will occur weekly from when approximately 500 participants have been followed for the primary outcome assessed at Day 20. To allow for the possibility that the proportion of hospitalizations or death is higher than anticipated, the first review of efficacy and safety data may occur earlier, when approximately 62 participants in the two arms combined have been hospitalized or have died (62 is the expected number based on 15% hospitalizations/deaths in the placebo arm and 10% in the HCQ and Azithro arm, with an interim sample size of 500 participants).

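### Death outcomes inherit the primary estimator (log proportions per risk stratum, inverse-variance pooled), which suits a 10-15% composite but is a poor default for a rare outcome

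*Protocol*

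**What the plan says.** Section 10.2.2 lists as its first secondary outcome "Death from any cause during the 21-day period from and including the day of the first (confirmed) dose of study treatment". Section 10.6.2 then groups three analyses: "The cumulative proportion of participants dying during the first 21 days of follow-up", death through 24 weeks, and the 24-week composite. All three "will be analyzed in a similar manner to the primary outcome".

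The primary method in section 10.6.1 starts from the Kaplan-Meier cumulative proportion in each arm of each risk stratum. Within a stratum, "the difference between randomized arms in the estimated log cumulative proportion will be calculated", with a Greenwood variance. The two stratum results are then combined, "weighted by the inverse of the stratum-specific variance of the difference".

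The event rates behind this choice are those of the composite: section 10.5 works with "15% hospitalizations/deaths in the placebo arm and 10% in the HCQ and Azithro arm". No death rate is given for either stratum or for the trial population. The only related figure is an all-case fatality of up to 3% in section 2.1. Section 10.6 introduces the methods with "The following provides an outline of the methods for the main comparisons between randomized arms" and leaves the detail to the SAP.

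**The concern.** The log of a zero proportion does not exist. Two strata and two arms give four cells. If one arm of a stratum has no deaths, that stratum's log difference and variance have no value, and neither does the pooled ratio, its confidence interval or its p-value. Even with deaths in every cell, a Wald test on the log ratio rejects too rarely when counts are small.

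Mortality will be read closely whatever the primary result. The plan could give up power for it unnecessarily. A workaround chosen only after an empty cell has been seen would also be a data-dependent choice.

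**Working it through.** **Inputs from the protocol.** 2000 participants, 1:1 allocation, two risk strata, at least 50% high risk targeted; composite 15% v 10% (ratio 0.667); two-sided 5%; 5% loss to follow-up.

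**Assumed.** A 50:50 stratum split (500 per cell), no censoring, and all stratum death rates.

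**1. The method works for the outcome it was built for.** With 950 evaluable per arm, the standard error of the log ratio is √(0.85/(950×0.15) + 0.90/(950×0.10)) = √0.01544 = 0.1243. Then log(1.5)/0.1243 = 3.26, and Φ(3.26 − 1.96) gives 90.4% power. An ordinary two-proportion test gives 91.0%. A simulation with four equally spaced O'Brien-Fleming looks gives 89.9% on the log-ratio scale. The stated 90% is reproduced.

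**2. Chance that an arm of the low-risk stratum has no deaths.** With control rate p0 and treated rate p1, this is 1 − [1 − (1−p0)^500][1 − (1−p1)^500]. For p0 = 0.5%, 0.995^500 = 0.082. Equal arms give 1 − 0.918² = 16%. At ratio 0.667 the treated arm is empty with probability 0.188, giving 1 − 0.918×0.812 = 25%.

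| Low-risk mortality | Equal arms | Ratio 0.667 |
|---|---|---|
| 0.2% | 60% | 69% |
| 0.5% | 16% | 25% |
| 1% | 1% | 4% |

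The chance exceeds 50% only below 0.245% mortality (0.305% at ratio 0.667). It is under 10% above 0.59% (0.76%).

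**3. Power for death.** Binomial deaths were simulated in four cells, 400,000 trials per scenario. Without censoring, Greenwood's formula gives a stratum variance of 1/a − 1/500 + 1/b − 1/500 for death counts a and b. The protocol names no rule for an empty cell, so two fallbacks were tried: drop the undefined stratum, or collapse the strata in those trials. The comparator is the stratified Mantel-Haenszel test.

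| Placebo mortality, low/high risk | RR | Planned, stratum dropped | Planned, strata collapsed | Mantel-Haenszel |
|---|---|---|---|---|
| 0.4/3% | 0.667 | 14.4% | 16.2% | 18.8% |
| 0.5/2% | 0.667 | 9.2% | 11.4% | 15.1% |
| 1/3% | 0.667 | 16.8% | 17.5% | 21.5% |
| 0.4/3% | 0.5 | 31.9% | 36.0% | 40.4% |
| 0.5/2% | 0.5 | 19.0% | 24.3% | 30.6% |
| 1/3% | 0.5 | 37.2% | 39.7% | 46.1% |

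The gain is about 4-6 points (RR 0.667) and 8-12 points (RR 0.5) if the stratum is dropped. It is about 3-4 and 4-6 points if strata are collapsed. At 1/5% mortality, which averages the protocol's 3%, it is about 3-4 and 4-5 points across the two fallbacks.

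**4. Null rejection.** In the first three scenarios it is 3.1-3.8% with the stratum dropped and about 3.6-4.1% with strata collapsed, against 4.9-5.2% for Mantel-Haenszel.

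**5. Is this only an empty-cell effect?** No. In trials where the planned estimator is defined, power at RR 0.5 is 31.2, 18.6 and 37.6% against 36.6, 26.1 and 44.2%. Null rejection there is 2.9-3.8% against 4.4-5.0%.

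**6. Is it specific to rare outcomes?** Yes. For the composite, with assumed placebo rates of 5% (low risk) and 25% (high risk), averaging 15%, and ratio 0.667, power is 93.7% against 93.8%. Null rejection is 4.9% against 5.0%.

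**The case against.** The strongest reply is that this belongs to the SAP. Section 10.6 is an outline, its wording asks only for similarity, and sparse-cell handling is ordinary SAP detail. A ratio of Kaplan-Meier proportions standardised over strata might already count as similar. That stands as a limit: the absence of a zero-event rule is not a fault in this protocol. What remains is that the protocol names a method for death, and the method as described is a poor default even where every cell has deaths. The same section uses stratum-adjusted binary regression for cardiac adverse events and for treatment discontinuation, so the plan already varies method by outcome.

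Second, no figure in the document supports a very low death rate, and the larger power gains depend on the fallback assumed. Both are correct, which is why the gain is given as a range.

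Third, the error is only towards caution, death is a secondary outcome, and power at the design ratio is low under every method (about 9-22% in the three main scenarios). Keeping the same scale as the primary analysis is also defensible. This limits the importance of the point but does not remove it.

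A reader might infer that the mortality analysis will fail in this trial. The documents do not support that: with 3% overall mortality split 1/5%, an empty cell is uncommon (about 4% of trials at ratio 0.667). A reader might also infer that interim stopping on death would break down. Section 10.5 mentions possibly applying the stopping guideline to death, but does not say which estimator would be used.

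**Conclusion.** The point holds as a minor one. The estimator carried over to death is undefined if one arm of a stratum has no deaths, and conservative when deaths are few. Against a stratified Mantel-Haenszel test the loss is about 3-6 points of power at RR 0.667 and 4-12 at RR 0.5, with null rejection of about 3-4% instead of about 5%. These figures rest on assumed stratum mortality, a 50:50 stratum split, no censoring and an assumed fallback for empty cells; with strata collapsed the gains are only 3-4 and 4-6 points. The primary outcome, the sample size and the trial's type I error are not affected. The check on the composite gives no reason to extend the point to the 24-week composite named in the same sentence.

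**What to change.** For the death outcomes only, state in section 10.6.2 or the SAP:

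- The p-value comes from a log-rank test stratified by risk group.
- The effect is a risk difference or ratio of Kaplan-Meier proportions, standardised over strata within each arm before the contrast is formed, with a delta-method variance.
- If a whole arm has no deaths, report the risk difference with a stratified exact test.
- Say whether the p-value or the confidence interval governs, because the two come from different methods and may occasionally disagree. In the same simulations the standardised log ratio had power between the planned method and Mantel-Haenszel (for 0.5/2% at RR 0.5: 27.0%, against 19.0% with the stratum dropped and 30.6%).

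The cost is a few sentences and a few lines of code, with no new data and no change to the primary analysis. The drawback is that the death analysis then differs in form from the primary one.

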1.3 Secondary Objectives

1.3.1 To determine safety of HCQ and Azithro including 1) adverse events (AEs) leading to early discontinuation of treatment with HCQ and Azithro and 2) cardiac AEs.

1.3.2 To determine if HCQ and Azithro reduce the frequency of detection and levels of SARS-CoV-2 RNA in site-collected nasopharyngeal (NP) swabs and self-collected nasal swabs in subset of participants.

1.3.3 To determine if HCQ and Azithro change the severity and duration of self-reported symptom experience of COVID-19.

1.3.4 To determine if HCQ and Azithro will prevent the composite endpoint of either hospitalization or death by 24 weeks after study entry. Hospitalization is defined as ≥ 24 hours of acute care.

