6.3.10 Study Diary

Distribution of Study Diary

Participants will be provided a Study Diary at study entry. The Study Diary is posted on the DMC Portal in the Forms Management Utility.

Participants will be asked to keep a log of symptoms, temperature (if possible), medications they are taking, and major events such as urgent visit to an emergency room or clinic and hospitalization in their Study Diary on Days 0-20. At study entry, participants will complete the Study Diary prior to study treatment initiation. Depending on timing of each participant's dosing, some may complete HCQ/Placebo study treatment on Day 7 instead of Day 6 and need to report a Day 7 dose. Participants will be asked to complete the diary each evening.

Review of Study Diary

The Study Diary will be reviewed by study staff with each participant at the remote and in-person visits described in the [SOE](#) and the participant's answers recorded in the Participant Study Diary eCRF. If feasible, prior to or during the remote study visits, sites will request that the participant send images of each of their study diary entries to be reviewed at the next study contact.

Participants who report worsening illness from any cause during the trial may be referred to their health care provider or closest emergency room. Such instances will be recorded at the time of the notification, and during follow-up to assess study endpoints, i.e., hospitalization or death.

Review of Treatment Adherence

The treatment adherence portion of the Study Diary will be reviewed by study staff with each participant at the remote and in-person visits (if applicable), as described in the [SOE](#). The participant's answers of timing of doses taken will be recorded in the Adherence Assessment eCRF. If any doses are missed, the reason for the missed dose will be recorded.

Collection of Study Diary

The Study Diary will be collected per the [SOE](#). **If Day 20 is conducted remotely, arrangements should be made for future transfer of study diary from the participant to the study staff (i.e., mailing the study diary or sending images).**

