- 10.2.2.9 Time to self-reported return to usual (pre-COVID) health.
- 10.2.2.10 Level (detectable versus not detectable, and continuous) of SARS-CoV-2 RNA from self-collected nasal and site-collected NP swabs at entry and Days 6 and 20 among subset.

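### Time to return to usual health is given descriptive statistics only, while the two parallel secondary durations get a between-arm test and a rule for hospitalisation and death

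*Protocol*

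**What the plan says.** Protocol section 10.2.2 lists "Time to self-reported return to usual (pre-COVID) health" as secondary outcome 10.2.2.9. It names no collection instrument, time horizon or censoring rule for it.

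Section 10.6.2 mentions fever duration, symptom duration and this outcome together, and says of the last that "duration of time to self-reported return to usual health will be summarized with descriptive statistics". The next sentence turns to comparison and covers only the first two: "Participant-specific durations of fever and symptoms will be compared between study arms using a two-sided stratified Wilcoxon test". For the symptom score, the "area under the curve (AUC) over time will also be compared using a two-sided stratified Wilcoxon test". Participants whose diary cards are incomplete because of hospitalisation or death "will be ranked in these analyses as having poorer outcomes than participants who survived without hospitalization". That ranking rule belongs to the Wilcoxon analyses, so it does not reach return to usual health.

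Section 10.6 describes itself as an outline of the main comparisons and leaves detail to a statistical analysis plan, which is not at hand.

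**The concern.** All three durations are listed secondary outcomes of a randomised, blinded trial. Two are compared between arms and one is not, and no reason is given.

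The one left out most needs a stated method. Outcomes 10.2.2.6 and 10.2.2.7 define fever and symptom duration as the last qualifying day on the diary card, so a participant with a complete diary has a value. A time to return does not exist for someone who has died or has not yet returned.

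Two things are at stake. An analysis that follows 10.6.2 as written reports this outcome with no randomised comparison, and a test added after unblinding would be post hoc. Separately, the wording leaves room for a summary of durations among returners only. That group is selected after randomisation, and such a summary can hide much of a real difference.

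**Working it through.** The protocol gives no figure for this outcome, so there is none to reproduce. The check has a textual part and an illustration.

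**Text, side by side (sections 10.2.2 and 10.6.2)**

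| Outcome | Between-arm test | Rule for hospitalisation or death |
|---|---|---|
| Fever duration (10.2.2.6) | Two-sided stratified Wilcoxon | Incomplete diaries ranked worse |
| Symptom duration (10.2.2.7) | Two-sided stratified Wilcoxon | Incomplete diaries ranked worse |
| Symptom-score AUC (10.2.2.8) | Two-sided stratified Wilcoxon | Incomplete diaries ranked worse |
| Return to usual health (10.2.2.9) | None stated | None stated |

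**Illustration: what a returners-only summary would do**

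From the protocol (section 10.4): about 1000 per arm and a 5% loss allowance, so 950 per arm. Assumed, not in the protocol: exponential return times, medians of 14 and 11 days, observation cut at *c* = 20 days, and no separate allowance for hospitalisation or death.

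Rate: r = ln 2 / median.
- 14 days: r = 0.0495, true mean 1/r = 20.20 days
- 11 days: r = 0.0630, true mean 1/r = 15.87 days
- True mean difference: 4.33 days

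Proportion returned by Day 20: F = 1 − exp(−20r).
- 14 days: 0.629
- 11 days: 0.716

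Mean among returners: 1/r − 20·exp(−20r)/F.
- 14 days: 20.20 − 20 × 0.3715/0.6285 = 8.38 days
- 11 days: 15.87 − 20 × 0.2836/0.7164 = 7.95 days
- Difference among returners: about 0.4 days

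A log-rank test on the same assumed data:
- Returns: 950 × (0.629 + 0.716) ≈ 1278
- Hazard ratio: 14/11 = 1.27
- Power: Φ(√(1278/4) × ln 1.27 − 1.96) ≈ 0.99
- With medians of 14 and 12 days, power is about 0.78.

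Sensitivity: hold the ratio at 1.27 and vary the control median from 8 to 28 days. True mean differences of 2.5 to 8.6 days shrink to 0.65 to 0.22 days among returners, and log-rank power stays at about 93% or more.

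The illustration shows what one permitted reading of the text would cost. It does not describe an analysis that the protocol specifies.

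**The case against.** The strongest reply is that this is detail for the statistical analysis plan. Section 10.6 is visibly incomplete as an outline: outcome 10.2.2.2 (death, hospitalisation or urgent visit) gets no method in 10.6.2 at all. Nothing promises a test for each of the ten secondary outcomes, and reporting a subjective supportive outcome descriptively is a legitimate choice. A Kaplan-Meier curve by arm is itself descriptive, so part of the fix already fits the wording.

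Much of this stands, and it keeps the point minor. It does not remove it. For this outcome the protocol is not silent: it states a non-comparative method and then tests the two durations named beside it. An analysis plan that adds a test would depart from that contrast, so the matter should be settled in advance.

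Three stronger readings are tempting, and the documents support none of them.

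- *The diary cuts this outcome off at Day 20.* Section 6.3.10 asks for major events such as "hospitalization in their Study Diary on Days 0-20", and says "Participants will be asked to keep a log of symptoms, temperature (if possible), medications they are taking". Return to usual health is not among the items listed, and 10.2.2.9 does not name the diary. Contacts continue at Weeks 12 and 24. A Day 20 limit is plausible but inferred.
- *The plan summarises returners only.* Section 10.6.2 says descriptive statistics and does not say on whom. It also recognises that a summary restricted to hospitalised participants would not be a randomised comparison.
- *Objective 1.3.3 cannot be answered.* That objective asks whether treatment will "change the severity and duration of self-reported symptom experience of COVID-19". It does not name return to usual health, and fever duration, symptom duration and symptom-score AUC all carry comparative tests for it.

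**Conclusion.** The point holds as a minor one. Section 10.6.2 fixes a non-comparative method for a listed secondary time-to-event outcome while testing its two companions, and it gives no rule for non-return, hospitalisation or death. Followed as written, it produces no between-arm comparison for outcome 10.2.2.9. This conclusion rests on the text alone.

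The possible understatement, 0.4 days shown against a true 4.3, is conditional. It needs a summary limited to returners, a Day 20 cut, exponential times and medians of 14 and 11 days, none of which the protocol states. It shows why the method should be named and is not an estimate of bias in this trial. The primary outcome and the other secondary comparisons are unaffected.

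**What to change.** In section 10.6.2, state that time to self-reported return to usual health:

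1. is summarised by arm with Kaplan-Meier estimates and compared with a two-sided test stratified by risk group;
2. is observed over a named period, the one over which the item is actually collected, with participants who have not returned censored at the end of that period;
3. counts hospitalised or dead participants as not returned through that period. They stay in the risk set to its end and are not censored at the date of the event.

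If a descriptive report is what the sponsor intends, say so with the reason, and still state items 2 and 3.

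The cost is a few lines of text and no design change. The sponsor should confirm which form collects the item and for how long, since the protocol does not say. The downside is one more secondary test without multiplicity adjustment, to be read as supportive.
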